
STUDY OBJECTIVES
	
Primary
 
 • To assess whether there are differences in return rates (compliance) between electronic and paper patient reported outcome (PRO) questionnaires at the first post intervention time point. 
Secondary
 
 • To investigate whether there are differences in response scores between the two modalities (electronic and paper) at key time points. • To assess whether there are differences in return rates (compliance) between paper and electronic questionnaires at later time points after the first post intervention questionnaire. • To investigate whether there are differences in number of items completed within a questionnaire (completeness) between electronic and paper questionnaires. • To investigate whether there are differences in satisfaction between participants filling out electronic or paper questionnaires • To investigate whether there are any demographic differences between people who agree to be randomised and those who choose to complete questionnaires electronically or on paper • To investigate whether changes in response scores from baseline (paper questionnaire) to follow-up vary according to modality of follow-up questionnaire completion. • To investigate the time taken to distribute paper questionnaires compared to electronic questionnaires. • To assess the requirement to remind patients to fill in paper and electronic questionnaires.

STUDY DESIGN
	
Partially randomised patient preference study within a trial (SWAT).

STUDY POPULATION
	
Participants in ICR-CTSU oncology trials which are hosting the SWAT (see appendices).

RECRUITMENT TARGET
	
Two-hundred and forty-four participants are required for the randomised comparison.
 
An estimated 366 participants, including those in the patient preference cohort, will be enrolled.

STUDY INTERVENTION
	
Modality of PRO questionnaire – electronic or paper.

PRIMARY ENDPOINT
	
Compliance with questionnaire completion, defined as the percentage of patients returning a questionnaire out of those expected (i.e. not withdrawn or died) at the first questionnaire time point after an intervention within the host trial.


SECONDARY ENDPOINTS
	
 • Domain scores and item responses at key QoL host trial time points. • Compliance with questionnaire completion at all further time points of QoL collection within the host trial. • Completeness of data (% of questions filled in within the questionnaire) in the host trial’s primary QoL questionnaire. • Patient satisfaction with electronic and paper questionnaires. • Patient demographics in each group • Change in response scores from baseline. • Time taken (minutes) to prepare a paper questionnaire for distribution compared to electronic dispatch. • % of patients sent reminders to complete questionnaires for paper and electronic questionnaires.

FEASIBILITY ENDPOINTS
	
 • The proportion of participants opting for a preference rather than randomisation after 50 participants have been enrolled. • The number of participants recruited after 6 months.

FOLLOW UP
	
Follow up questionnaires will be administered at time points determined by the host trial.
 
Questionnaires will be administered for the purposes of the SPRUCE study up to 12 months post study entry, after which PRO data will continue to be collected within the host trial as appropriate. Data collected within SPRUCE will be shared with the host trials for the purposes of trial specific PRO analyses.
 
Participants will be sent a demographics questionnaire for completion after study entry in their chosen/allocated format.
 
SPRUCE participants will receive a paper questionnaire regarding satisfaction with questionnaire method 14 months after study entry.

STUDY SCHEMA

1. INTRODUCTION

Within healthcare and clinical trials, questionnaires can be used to collect information directly from patients on the impact that treatment and health conditions may be having upon their quality of life. These data are known as patient reported outcomes (PRO) and are defined as “any report of the status of a patient’s health condition that comes directly from the patient, without interpretation of the patient’s response by a clinician or anyone else”(1). A wide range of validated questionnaires are used to collect PRO, covering general health items as well as more disease specific factors.

Within oncology trials, the patient perspective and survivorship effects are crucial factors to consider in evaluation of new treatments (2). Quality of life (QoL) information is thus a key factor to consider in their adoption and implementation. At many clinical trials units, including the Institute of Cancer Research Clinical Trials Statistical Unit (ICR-CTSU), QoL information is currently captured with paper PRO questionnaires to inform primary and key secondary end points of clinical trials. Collection of PROs is a time consuming and laborious process requiring significant input from both patients, hospital staff and clinical trials units often over an extended period of time. Streamlining this process with the use of technology in the form of electronic PRO (ePRO) questionnaires has the potential to increase patient convenience, improve patient experience, reduce administrative burden, save costs, increase patient compliance and avoid secondary data errors including those due to data transcription, leading to more accurate and complete data (3)(4).

Over the past decade, advances in information technology and improved access to the internet have led to a rapid increase in the use of electronic devices including smartphones, tablets and laptops. In 2019 91% of adults in the UK had regular use of the internet (5), with the over 65s having a striking increase in internet use from 2011 to 2019. The effect of the COVID-19 crisis is likely to have increased internet exposure further and it has already been shown that the proportion of online adults aged over 65 who make a least one video-call each week increased from 22% in February 2020 to 61% by May 2020 (6).

Although ePRO questionnaires have been widely studied in the general clinical setting it is yet to be proven that they are as effective as paper PRO questionnaires at collecting data within clinical trials where there are additional research ethics, research governance and regulatory requirements to comply with. Our study will pilot implementation of ePRO collection within ICR-CTSU trials and generate evidence regarding its equivalence to paper-based collection. This research will investigate whether ePRO questionnaires can be used within multicentre clinical trials and reduce the burden of clinical trial follow up on patients, allowing patients to participate in quality of life follow up with the minimum possible inconvenience at a time when the patient is already under the stress of being unwell. If this is the case the impact could allow for more comprehensive quality of life study recruitment and responses, helping ensure the patient experience is captured as accurately as possible over the appropriate duration of time.

1.1. BACKGROUND

There has been extensive work conducted across different medical specialities to establish the intra-patient equivalence of paper and electronic based questionnaires within participants and their validity for data collection in a clinical setting. Muehlhausen et al (7) conducted a systematic review and meta-analysis of the equivalence of patient reported outcome measures administered by electronic and paper formats. The review included 72 studies, showing overall equivalence between the two formats when completed by the same patients. This was an update of a previous review by Gwaltney et al conducted in 2008 (8), which also showed equivalence within participants. Following on from these two meta-analyses, further studies have added weight to the finding of equivalence of data following migration from original paper to electronic format. Participants of these studies had the equivalence

of scores compared between their completion of both paper and electronic questionnaires, with a paper test retest arm as the control (9) (10).

Patient compliance with ePRO questionnaires and the completeness of data returned is essential for clinical trials. One factor that may increase questionnaire return rates and improve the patient experience is to reduce the amount of time required to complete. Park et al showed within the clinical outpatient setting that time taken to complete the electronic form was significantly shorter than that required for the paper version (11). Some studies have shown 83% compliance with ePRO questionnaires in the clinic, with between 76 and 95% of patients finding the system usable and recommending it to others (12)(13). On the other hand, studies in a surgical setting found poor uptake of ePRO questionnaires amongst participants offered the option. In a recent report from 2019 only 12% of 642 participants opted for completion of e-PRO in one study and 34% of 1296 participants opted for it in another. Overall, 280 of ~5700 (~5%) questionnaires were completed electronically, with the remainder completed by post or in clinic(14).

There are two significant limitations of literature published to date. Firstly, although ePRO questionnaires are becoming increasingly popular for use in clinical trials, there is limited evidence of patient uptake and compliance in this setting, and none from randomised studies. One trial including rheumatoid arthritis patients within two randomised control trials asked patients to fill in electronic diaries. This study showed high compliance of up to 93% of patients over 12 weeks, however there was the lack of a control group filling out paper questionnaires, meaning it is not possible to be sure the compliance was non-inferior to paper diaries (15) .

The second limitation is the lack of information as to whether completeness of data is equivalent or superior in the electronic format. One recent study in a healthy university undergraduate population (16) did assess data capture in electronic and paper versions with participants of a prospective study being given the opportunity to choose the format for completion of a food intake based questionnaires at baseline and 10 year follow up. The results were mixed, with increased missing data in some subsections in the electronic version with improved data levels in other subsections. The paper concluded that data capture was equivalent. However, these results may not be applicable in a patient population, particularly in oncology where patients can be unwell and more likely to be in the older section of the population. There are a limited number of other studies that performed randomised group studies but these again are largely in either the mental health, general healthy or paediatric population (17)(18) and therefore not directly applicable to oncology patient population.

1.2. DESCRIPTION OF POPULATION

The study population includes all patients recruited to an ICR-CTSU host trial within which SPRUCE is embedded. All participants will be UK cancer patients aged at least 16 years old.

1.3. STUDY RATIONALE

The proposed study aims to assess the effectiveness of using electronic questionnaires to collect PROs, exploring the potential for improving collection of PROs for future assessment of impact of health interventions on trial participants.

2. STUDY OBJECTIVES

2.1. PRIMARY OBJECTIVE

The primary objective is to assess whether there are differences in return rates (compliance) between electronic and paper PRO questionnaires at the first post intervention time point.

2.2. SECONDARY OBJECTIVES

- To investigate whether there are differences in response scores between the two modalities (electronic and paper) at key time points (e.g. due to convenience of returning ePRO questionnaires more severe PRO issues may be identified electronically).
- To assess whether there are differences in return rates (compliance) between paper and electronic questionnaires at later questionnaire time points.
- To investigate whether there are differences in number of items completed within a questionnaire (completeness) between electronic and paper questionnaires.
- To investigate whether there are differences in satisfaction between participants filling out electronic or paper questionnaires
- To investigate whether there are any demographic differences between people who agree to be randomised and those who choose to complete questionnaires electronically or on paper
- To investigate whether changes in response scores from baseline (paper questionnaire) to follow-up vary according to modality of follow-up questionnaire completion.
- To investigate the time taken to distribute paper questionnaires compared to electronic questionnaires.
- To assess the requirement to remind patients to fill in paper and electronic questionnaires.

2.3. FEASIBILITY OBJECTIVES

- To assess patient acceptance of randomisation between questionnaire modalities.
- To assess feasibility of recruitment.

3. STUDY DESIGN

This is a study within a trial (SWAT) which will be run in multiple ICR-CTSUs to include participants affected by a range of cancers representative of those in ICR-CTSUs' trial portfolio.

SPRUCE is a partially randomised patient preference study investigating electronic versus paper PRO collection.

Following enrolment into a host trial, eligible participants will be approached regarding taking part in the SPRUCE study. Patients who provide written informed consent to join SPRUCE will either be:

- Randomised 1:1 between electronic and paper PRO questionnaire completion

OR

- Registered for electronic or paper PRO questionnaire completion

Whether a participant is randomised or registered will be determined by patient preference.

The study has two formats depending on the host trial within which it is embedded:

- Format A:

Applicable where a host trial does include patient reported outcome measures within the approved trial protocol. The instrument used to capture the host trials' primary PRO endpoint will be the key questionnaire of interest in SPRUCE. PRO data for host trial participants who are also participating in SPRUCE will be collected within SPRUCE (and not within the host trial)

and the questionnaire schedule and content will follow that of the host trial. Data will be shared with the host trial for the purpose of the host trial's PRO analysis. Details of each host trial will be set out in an appendix to this protocol.

- Format B:

Applicable where a host trial does not include patient reported outcome measures within the approved trial protocol. The EORTC QLQ-C30 will be administered at time points selected to fit the host trials' patient pathway. Details of each host trial will be set out in an appendix to this protocol.

4. STUDY ENDPOINTS

4.1. PRIMARY ENDPOINT

Compliance with questionnaire completion, defined as the percentage of patients returning a questionnaire out of those expected (i.e. not withdrawn or died) at the first quality of life assessment time point after completion of the host trial's study intervention.

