7.5. DISCONTINUATION OF PARTICIPATION

Participants may discontinue from participation in SPRUCE at any time at their own request. Participants who cease participation will continue to be followed up in the QoL sub study within the host trial for format A, unless they specify otherwise.

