8. STATISTICAL CONSIDERATIONS

8.1. STATISTICAL DESIGN AND SAMPLE SIZE JUSTIFICATION

This is a partially randomised patient preference study, allowing participants to choose a preferred modality for questionnaire completion if they are unwilling or unable to be randomised between electronic or paper questionnaires. The randomised and patient preference groups will be analysed separately.

Sample size estimates are based on numbers required for the randomised part of the study. Based on compliance reports from existing ICR-CTSU trials, return rates for paper questionnaires are expected to be in the region of 90% at the first post intervention time point. 244 patients would therefore be required to be randomised (1:1) to exclude $\leq 80\%$ compliance rates with ePRO (i.e. 10% non-inferiority margin), with 80% power and 1-sided $\alpha=0.05$.

We have assumed that approximately two-thirds of patients entering the SWAT will agree to be randomised thus anticipate needing to recruit 366 patients overall (244 randomised and 122 preference).

The proportion of participants opting for allocation via randomisation versus preference will be monitored throughout SPRUCE; if the numbers in the randomisation cohort are lower than anticipated then the study design may be changed to offer all patients the choice of electronic or paper questionnaires (see Section 8.4).

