8.3. STATISTICAL ANALYSIS PLAN

The randomised and patient preference cohorts will be analysed separately for all endpoints as confounders including patient baseline characteristics (e.g. age, sex) will need to be taken into account for the comparisons between electronic and paper questionnaires in the non-randomised patients. Regression analyses will adjust for potential confounders such as patient demographics and clinical characteristics for the comparison of outcomes between the patient preference groups. Additionally, descriptive analyses will summarise demographic and clinical characteristics of patients opting for randomisation versus expressing a preference.

The primary outcome of compliance at the first post intervention time point within the host trial will be calculated as percentage of returned questionnaires out of those expected (i.e. not withdrawn or died) for the electronic and paper questionnaire groups, and the difference calculated along with a 2-sided 90% confidence interval. Non-inferiority for electronic questionnaires will be concluded if the lower confidence limit for the difference in compliance for electronic versus paper questionnaires is greater than -10%.

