8.4. INTERIM ANALYSES AND STOPPING RULES

The number of patients opting for a preference rather than allocation via minimisation will be monitored monthly and assessed after 50 patients have been recruited. If greater than 50% of participants have declined allocation via minimisation, or subsequently declined allocated modality, consideration will be given to ceasing randomisation and adopting an alternative recruitment and analysis strategy.

The overall feasibility of recruitment for the study will be monitored and re-evaluated if a third of the required patients have not been recruited within 6 months of the study commencing. If recruitment was an issue at that point, the decision to increase the number of sites that the SWAT is run at or to embed the SWAT into further ICR-CTSU trials could be taken to improve recruitment.

Impact of SPRUCE on PRO uptake and drop out in host trials will be monitored to ensure that PRO data collection within the host trial is not adversely affected by the SWAT. Under format A this will consider the number/proportion of patients consenting to provide PRO data pre and post implementation of SPRUCE.

An interim analysis to review emerging data is planned between 12-18 months after the trial opens and will include the facility to include data in a confidential PhD thesis. Analyses will follow the main statistical analysis plan, although may be largely descriptive if the number of patients are insufficient for formal statistical analysis. Results will be confidential and only for the purposes of the PhD.

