11.2. DATA ACQUISITION

Participants will complete an initial questionnaire booklet on paper, then further questionnaires will be completed in accordance with their randomly allocated or preferred format. All participants will be sent a demographics questionnaire following study entry.

Participants completing questionnaires electronically will receive invitations at the required time points, with a personalised email link sent to the patient for electronic questionnaire completion. ICR-CTSUS will provide guidance to participants to aid the completion of questionnaires. If the questionnaires are not returned within a reasonable time frame, a reminder email will be sent to participants. If two consecutive questionnaires are not completed within a reasonable time frame, a change in participation email will be sent, prompting the participant to inform the ICR-CTSUS team if they no longer wish to participate in the study.

Participants completing questionnaires on paper will receive booklets by post by the ICR-CTSUS following confirmation from the participating site that the patient is alive and able to fill in the questionnaire. Completed booklets will be posted to ICR-CTSUS for data entry. If the questionnaires are not returned within a reasonable time frame, a reminder letter will be sent to participants. If two consecutive questionnaires are not completed within a reasonable time frame, a change in participation letter and form will be sent, prompting the participant to inform the ICR-CTSUS team if they no longer wish to participate in the study.

If necessary, ICR-CTSUS may ask sites to administer the questionnaire for the first post-intervention time point.

A participant satisfaction survey will be sent by ICR-CTSUS to all participants for completion on paper 14 months after joining the study.

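### The primary compliance rate drops participants who have withdrawn without saying from what, so modality-driven exits from SPRUCE leave the denominator and can favour non-inferiority

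*Protocol*

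**What the plan says.** The protocol summary and section 4.1 give the same denominator for the primary endpoint: compliance is "defined as the percentage of patients returning a questionnaire out of those expected (i.e. not withdrawn or died"). Section 8.3 carries it into the analysis as the "percentage of returned questionnaires out of those expected (i.e. not withdrawn or died) for the electronic and paper questionnaire groups". It then sets a threshold of -10% for a two-sided 90% interval and fixes the decision by it: "Non-inferiority for electronic questionnaires will be concluded if the lower confidence limit for the difference in compliance for electronic versus paper questionnaires is greater than" that threshold.

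No section defines withdrawal for this purpose. The only exit the protocol describes is from SPRUCE itself. Section 7.5 allows it at any time at the participant's request and adds: "Participants who cease participation will continue to be followed up in the QoL sub study within the host trial for format A", unless the participant says otherwise.

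Two other sections touch on the subject. Section 8.4 sets a trigger for reviewing whether to go on randomising: "If greater than 50% of participants have declined allocation via minimisation, or subsequently declined allocated modality". Section 11.2 says that after two consecutive missed questionnaires "a change in participation email will be sent, prompting the participant to inform" the trials unit if they wish to stop; the paper arm gets a letter and form instead.

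**The concern.** The study asks whether electronic collection obtains questionnaires as reliably as paper. A format A participant who leaves SPRUCE because the allocated format does not suit them still has a questionnaire due, in the host trial. What has ended is collection by the allocated modality. For this study's question that is a failure of the modality, yet the definition takes the person out of both numerator and denominator.

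The primary comparison thus conditions on an event that occurs after randomisation and that the allocation can cause, so it no longer compares the groups as randomised. Removing such people raises the observed rate most in the arm that people leave most. If that is the electronic arm, the error runs towards declaring non-inferiority.

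**Working it through.** **Inputs.** From sections 8.1 and 8.3: 244 randomised 1:1, so 122 per arm; paper compliance as in "return rates for paper questionnaires are expected to be in the region of 90% at the first post intervention time point"; margin 10 points; one-sided alpha 0.05; power 80%; lower limit of a two-sided 90% interval. Withdrawal proportions by arm are not given; they are assumed here over a range.

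**1. The planned sample size.** The Farrington-Manning formula with 90% in both arms and restricted null rates 0.931 and 0.831 gives, per arm,

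n = [1.645·√(0.931×0.069 + 0.831×0.169) + 0.842·√(2×0.90×0.10)]² / 0.10² ≈ 121.1, rounded up to 122, or 244 in total.

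The stated 244 reproduces with no allowance for withdrawal.

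**2. Chance of declaring non-inferiority at the margin.** Let the true proportions collected among all randomised be 80% electronic and 90% paper, so that a correct test declares non-inferiority 5% of the time. Let wE and wP be the proportions withdrawn, none of whom return a questionnaire. The rates as the protocol defines them are

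pE = 0.80/(1 − wE), pP = 0.90/(1 − wP), with nE = 122(1 − wE), nP = 122(1 − wP).

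Then P(declare) = Φ[(pE − pP + 0.10)/SE − 1.645], with SE = √[pE(1 − pE)/nE + pP(1 − pP)/nP].

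Example, 5%/0%: pE = 0.80/0.95 = 0.842, nE = 115.9, difference −0.058, SE = 0.0434. This gives Φ(0.0421/0.0434 − 1.645) = Φ(−0.675) = 25%.

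| Withdrawn, electronic / paper | Observed electronic | Observed paper | P(declare) |
|---|---|---|---|
| 0% / 0% | 80.0% | 90.0% | 5.0% |
| 2% / 2% | 81.6% | 91.8% | 4.5% |
| 5% / 5% | 84.2% | 94.7% | 3.8% |
| 3% / 5% | 82.5% | 94.7% | 1.4% |
| 3% / 2% | 82.5% | 91.8% | 6.7% |
| 5% / 3% | 84.2% | 92.8% | 9.7% |
| 5% / 0% | 84.2% | 90.0% | 25% |
| 8% / 3% | 87.0% | 92.8% | 28% |
| 8% / 0% | 87.0% | 90.0% | 51% |

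The imbalance between arms drives the error. Equal withdrawal is slightly conservative, and excess paper withdrawal clearly so.

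**3. A single data set.** Paper returns 110/122 = 90.2%. In the electronic arm six people leave SPRUCE and 104 of the remaining 116 return.

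- As defined: 104/116 = 89.7%, difference −0.5 points, lower limit −0.0051 − 1.645×0.0391 = −6.9%. Non-inferiority is declared.
- All randomised: 104/122 = 85.2%, difference −4.9 points, lower limit −0.0492 − 1.645×0.0419 = −11.8%. It is not declared.

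In this example six leavers decide the result.

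**4. Cost in power of counting leavers as non-returns.** By simulation (200,000 runs, Wald interval, 90% return among those who stay in each arm), the chance of declaring non-inferiority is 84% with no withdrawal. At 2%/2% it is 83% under the present definition and 79% when leavers count as non-returns.

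**The case against.** Returned out of expected is a coherent measure of compliance, and leaving out deaths and host-trial withdrawals is defensible. People unwilling or unable to be randomised can join the preference cohort (sections 5.5 and 8.1), so those randomised have accepted either format. That makes heavy early withdrawal over modality less likely. The larger figures above need attrition that is markedly lopsided, and nothing in the protocol shows that it will be. A statistical analysis plan might define withdrawal and add an all-randomised sensitivity analysis. All of this limits the expected size. It does not repair a primary definition that the protocol fixes in three places.

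Three stronger readings are tempting and are not supported:

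- That the section 11.2 prompt turns primary non-responders into withdrawals. It follows two consecutive misses, whereas the primary endpoint is the first post-intervention questionnaire and baseline is completed before entry. Someone who misses that first questionnaire already counts as a non-return. The prompt could act earlier only if two questionnaires fell due before the primary one, and the host schedules are not in the protocol. It bears mainly on later time points.
- That section 8.4 removes people who decline their modality. It shows only that such refusal is foreseen; no text equates it with withdrawal, and a person who declines but stays in SPRUCE remains expected.
- That the definition will produce false non-inferiority. It can, if withdrawal is commoner in the electronic arm; the direction reverses if it is commoner on paper.

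**Conclusion.** The point holds in this form. The primary denominator excludes withdrawn participants without separating exit from SPRUCE from exit from the host trial, and section 7.5 supplies a route by which dissatisfaction with the modality becomes exclusion from the primary analysis.

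The size rests on withdrawal rates that the protocol does not give. At a true deficit exactly on the margin, the chance of wrongly declaring non-inferiority stays near the nominal 5% when withdrawal is equal, about doubles at 5%/3%, and reaches a quarter to a half at 5%/0% to 8%/0%. The calculation assumes that those who leave would otherwise count as not collected by their allocated modality. The sample size of 244 is not itself in error. Because the decision rule is applied directly to this rate and a few leavers can decide it, the definition should be changed before analysis.

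**What to change.** In the summary, section 4.1 and section 8.3:

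- Define the primary denominator as all randomised participants, in the arm as randomised, who are alive and have not withdrawn from the host trial when the first post-intervention questionnaire is due. Tying this to the host trial, and not to its questionnaire follow-up, lets it work for format B hosts, which have no such follow-up. It also keeps in anyone who stops all questionnaires but stays in the host trial.
- Count as not returned anyone who, before that date, left SPRUCE, or who did not return by the allocated modality because they declined it.
- Report withdrawals from SPRUCE and from the host trial by arm.
- Keep the present rate, among those not withdrawn, as a supplementary analysis.

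The change is one of wording. It needs host-trial status at the due date, and the appendices already provide for linkage by host trial ID. It has two costs. Compliance will read slightly lower than in the reports behind the 90% assumption. Power will also fall modestly, from about 84% with no withdrawal to about 79% at 2%/2%, because 244 carries no allowance for withdrawal. The sponsor should either accept that loss openly or revisit the number randomised.
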